7.7. Routine Adverse Event Reporting

All Adverse Events must be reported in routine study data submissions to the Principal Investigator on the toxicity case report forms. AEs reported through expedited processes (e.g., reported to the IRB, FDA, etc.) must also be reported in routine study data submissions.

7.8. Reporting to drug manufacturer

Version Date: April 18, 2023

The sponsor will promptly report all adverse events related to the Investigational Drug to Usona as agreed per the contract and set forth below.

Format of Transfer

Data should be transferred in one of the following formats if possible:

- CDISC ODM XML file (preferred)
- Comma Separated Value file

If the study's data collection procedures do not enable export in one of these formats, the Investigator agrees to work with Usona to identify a mutually agreeable format in which required data can be transferred to Usona.

Data Requirements

Category	Timing	Minimum data to be reported
Dosing	End of Study	Dates and times of doses
Information		Treatment received
		Dose received
Adverse Events	End of Study	AE Name
(AEs)		Discovery (spontaneous or solicited)
		Start date
		End date or ongoing
		Severity
		Relationship to study drug
		Action taken
		Resolution
		Seriousness
Concomitant	End of Study	Medication
Medications		Dose
		Dose frequency
		Start date
		End date
		Indication
Serious Adverse	Immediate	Full case report enabling completion of MedWatch
Events (SAEs)	(within 5 days of	Form 3500. Transmit to: [name]
	knowledge)	usonainstitute.org; [contact]
Pregnancy	Immediate	Initial report
	(within 5 days of	Gravidity
	knowledge) &	Parity
	follow-up through	Estimated delivery date
	30-days post-	Prenatal care (including initiation relevant to
	delivery or first	gestation)
	well-child visit	Pregnancy complications and dates

Medications used during pregnancy Follow-up report: Delivery Gravidity Parity Estimated delivery date Pregnancy outcome Date of delivery Duration of labor Type of delivery Postpartum complications Infant birth weight Apgar scores (1 min, 5 min) NICU admission Complications of newborn during hospitalization Date of hospital discharge or death Birth defects noted at birth Follow-up report: Well Child Visit Summary of diagnostic tests Complications Updates on past findings/anomalies

A serious adverse event (SAE) is an adverse drug or biologic or device experience occurring during any study phase (i.e., screening, admission, treatment, or follow-up), and at any dose of the study drug, comparator or placebo, that results in one or more of the following criteria:

- Results in death
- Is life-threatening*

Version Date: April 18, 2023

- Requires in-patient hospitalization (i.e., admission) or prolongation of existing hospitalization
- Results in persistent or significant disability** or incapacity
- Is a congenital abnormality or birth defect (in an offspring)
- Is an important medical event that may not result in death, be life-threatening, or require or prolong hospitalization may be considered an SAE when, based upon appropriate medical judgment, the event may jeopardize the subject or may require medical or surgical intervention to prevent one of the outcomes listed above. Examples of important medical events include events requiring intensive treatment in an emergency department, or convulsions that do not require in-patient hospitalization, or the development of drug dependency or drug abuse.

^{*} Life-threatening SAE: Any AE that places the subject, in the view of the investigator, at immediate risk of death from the reaction as it occurred; it does not include a reaction that, had it occurred in a more severe form, might have caused death.

** **Definition of disability:** A substantial disruption of a person's ability to conduct normal life functions.

8. PHARMACEUTICAL INFORMATION OF PSILOCYBIN

A list of the adverse events and potential risks associated with the investigational agent administered in this study can be found in Sections 7.1 and 7.2.

8.1. Psilocybin background

Version Date: April 18, 2023

Psilocybin 3-[2-(dimethylamino) ethyl]-1H-indol-4-yl] dihydrogen phosphate is a natural product produced by numerous species of Psilocybe mushrooms. The phosphate group is enzymatically cleaved in the body to produce psilocin, an agonist at a variety of serotonin receptors, the most important of which, for its behavioral effects, is the 5-HT2A receptor. Psilocybin was first isolated from Psilocybe mushrooms in 1957, followed by de novo synthesis in 1958. It was marketed worldwide in the 1960s as Indocybin for experimental and psychotherapeutic purposes. Although it was well tolerated and demonstrated potentially useful effects, it was classified as a controlled substance in the U.S., placed in Schedule I in 1970, and effectively removed from clinical use or scientific study. Psilocybin, and similar drugs such as lysergic acid diethylamide (LSD) and mescaline, fall into a pharmacological class that we refer to in this application as "classic psychedelics" to differentiate them from other psychoactive substances (ex. 3,4-methylenedioxy-methamphetamine; MDMA) that have different psychological/behavioral effects and different adverse effect profiles and risk/benefit ratios than psilocybin.

Several lines of evidence suggested that serotonergic hallucinogens, such as psilocybin, have clinical potential for inducing therapeutically-beneficial behavior change in a variety of psychiatric conditions and in individuals with psychological distress associated with a serious medical illness.

8.2. Importance of a Supportive Set and Setting Protocol

Due to the psychoactive nature of psilocybin, the safety of participants in clinical trials can be enhanced by testing psilocybin within a "set and setting" protocol (Lyons & Carhart-Harris, 2018).⁶⁹ By addressing the set (the emotional/cognitive/behavioral state/mindset and expectations of study participants just prior to psilocybin exposure) and setting (the physical environment in which the exposure occurs) of the experience, the risk of the subject reporting an event which was distressing or injuring themselves can be reduced. This approach generally incorporates three components: 1) preparation, 2) drug session, and 3) post session meetings to integrate the classic hallucinogen experience.

In the first phase, participants undergo pre-exposure preparation sessions designed to build rapport with the facilitators who would be present during the drug exposure session and to identify personal themes and struggles that might be especially likely to impact the session experience. In the second phase, the drug session itself is conducted by two facilitators who are present throughout the session. Sessions are typically conducted in a room designed to be quiet,

comfortable, and aesthetically pleasing, and participants are encouraged to wear eyeshades and listen to a program of music through headphones during the drug exposure to aid them in focusing their attention inward. In the third phase, participants are engaged in a series of drug-free interview meetings of variable frequency, sometimes over a period of several weeks, to discuss their session experience thoroughly with the goal of maximizing its therapeutic benefit.

8.3. Description

Psilocybin is a tryptamine derivative. Its chemical name is [3-[2-(dimethylamino)ethyl]-1H-indol-4- yl] dihydrogen phosphate. The molecular structure is the following:

Figure 8.1-1: Molecular structure of psilocybin

Following oral administration (0.224 mg/kg) of psilocybin, average blood concentration of the active metabolite psilocin was calculated to be 8.2 ± 2.8 ng/mL after 105 ± 37 minutes, yielding an estimated dose-normalized bioavailability of psilocybin to be $52.7 \pm 20\%$ (N = 3). Psilocin typically appears in plasma within 15 minutes after oral administration. Psilocin half-life following oral administration of psilocybin was found to be approximately 3 ± 1.1 hours and is detectable for up to 24 hours after administration.^{3,4} The levels of psilocin peaked at approximately 80 minutes, but the peak psilocin concentration was more gradually attained in some subjects than in others, suggesting metabolism rates can vary between individuals.³

Psilocin is metabolized to 4-hydroxyindole-3-acetic acid by deamination and demethylation via liver enzymes such as monoamine oxidase, and aldehyde dehydrogenase (Figure 8.1-2).⁴ Psilocin is also extensively glucuronidated by the UDP- glucuronosyltransferase (UGT) family of enzymes, with the highest glucuronidation activity demonstrated by UGT1A10.⁷⁰ The amount of psilocin glucuronide-excreted renally has been shown to exceed that of psilocin over a 24-hr time period, and analysis of psilocin in urine over 24 hours after a single dose has shown that less than 4% of the overall clearance of psilocin occurs through renal excretion.⁷¹The pharmacokinetics of psilocybin (as psilocin) are linear over the dose range of 0.3–0.6 mg/kg.^{3,71}

Figure 8.1-2: Metabolism of psilocybin

8.4. Form

For use in Usona sponsored clinical studies, psilocybin is provided as 25 mg capsules (size 2, hydroxypropyl methyl cellulose (HPMC), white)

4-hydroxytryptophol (4-HTP)

4-hydroxyindol-3-yl-acetic acid (4-HIAA)

8.5. Storage and Stability

Version Date: April 18, 2023

Psilocybin capsules are packaged individually into high-density polyethylene bottles (30 cc). Bottles must be maintained at room temperature.

Psilocybin presents as a white crystalline solid with a melting point of 220-228°C. It is stable over extended periods in dark storage at controlled room temperature. Psilocybin is soluble in 20 parts boiling water or 120 parts boiling methanol.

8.6. Compatibility

Not applicable

8.7. Handling

Psilocybin is a controlled substance listed in Schedule I. Capsules of psilocybin will be maintained in a locked, substantially constructed cabinet in a secured location, in accordance with Drug Enforcement Agency (DEA) regulations. In accordance with these requirements, the

Schedule I license holder, and pre-defined authorized individuals trained by the license I holder, will be responsible for storing, dispensing, and administering the psilocybin.

8.8. **Availability**

Psilocybin will be provided by Usona Institute at no cost and the study sponsor ([name], MSc) will order the drug once all regulatory requirements are approved. The study will cover the shipping costs.

8.9. **Preparation**

Not applicable

8.10. Administration

Capsules will be administered orally, with water, per the associated clinical protocol. Capsules should not be opened or chewed.

In case a patient vomit after the drug is administered, assuming the pill was swallowed and entered the stomach (not just gagging on the capsule and spiting an intact capsule back out) – we will not administer another capsule because in theory they might have ingested some portion of the Investigational Product. We will record whether the capsule is present in the emesis and make note of that in patient's records. This then would be an exception in dosing practices and likely will be an outlier.

8.11. Ordering

Psilocybin is not commercially available. It will be obtained through Usona Institute, a nonprofit medical research organization founded in 2014. Usona Institute conducts and supports biochemical and clinical research to further the understanding of the therapeutic effects of psilocybin and other consciousness-expanding medicines. Usona has developed psilocybin for oral administration (25 mg, single-dose) in conjunction with a supportive set and setting protocol for major depressive disorder (MDD). Additional information about Usona can be found at www.usonainstitute.org and in the Investigator Brochure.

The study drug will be shipped to and logged at Care Dimensions facility (Lincoln house). Authorized individuals will dispense the study drug after the order is transmitted from the study psychiatrist with name, date of birth and medical record number of the study participant. Dispensed drug will be obtained by the study team who will sign a log kept in the same cabinet the study drug is stored to ensure that all study drug is accounted for.

8.12. Accountability

The investigator, or a responsible party designated by the investigator, will maintain a careful record of the inventory and disposition of the study drug in a drug accountability record form along with any DEA required forms

8.13. Destruction and Return

Version Date: April 18, 2023

Expired or unused supplies of psilocybin will be returned to Usona or destroyed according to controlled substance disposal and institutional guidelines. Return or destruction will be documented on the drug accountability record form and any DEA-required forms.

9. CONCOMITANT MEDICATIONS AND TAPERING INSTRUCTIONS

If the participant is being treated with psychiatric drugs at the time they are recruited into the study, they will discuss medication tapering with the study psychiatrist and the hospice physician. If needed, the drugs will then be tapered in an appropriate fashion to avoid withdrawal effects. They will be discontinued long enough before the first Experimental Session to avoid the possibility of any drug-drug interaction (the interval will be at least five times the particular drug and active metabolites' half-life).

The therapists will request information about any changes in medication just prior to all intervention sessions. The study psychiatrist will be responsible for reviewing and confirming all medications collected during the study.

All medications, over the counter (OTC) and prescription will be collected from screening through V5. Throughout the protocol all medications used to treat AEs will be collected and all changes including discontinuations or additions to psychiatric medications will be collected. Medications will be recorded on the concomitant medications CRF.

In general, any MAOi will require a washout of at least 14 days or five half-lives of the medication or active metabolite (whichever is greater) plus one week for symptom stabilization. The Medication Tapering Table includes phenelzine, an example MAOi, (half-life of 11.6 hours) with a minimum of 14-day washout as requested. However, this table is not exhaustive. The washout time for any drug not listed on the table will be at least 5 times the half-life of the drug or active metabolite, plus 1 week for symptom stabilization.

Participants must be willing to refrain from taking any contra-indicated psychiatric medications during the active portion of the study.

As we expect individuals on hospice to be receiving medications to control symptoms such as pain, nausea and anxiety, all efforts will be made to not disrupt a patient's medication regimen unless the medication is contraindicated or carries a risk of interfering with psilocybin. Medications, such as opioids, may be given to patients during the trial to control pain, with efforts being made to not administer medications during the peak effect of psilocybin.

Medication Tapering Table

Version Date: April 18, 2023

Generic Name	Brand Name	Half-life (hours)	Days for Washout
		Including Active Metabolites	
alprazolam	Xanax	11	3
aripiprazole	Abilify	75	16
atomoxetine	Strattera	5-24	5
bupropion	Wellbutrin	21	5
citalopram	Celexa	35	8
clonazepam	Klonopin	30-40	8
diazepam	Valium	20-70	15
duloxetine	Cymbalta	12	3
escitalopram	Lexapro	32	7
fluoxetine	Prozac	7-9 (days)	45
imiprimine	Tofranil	6-18	4
lamotrigine	Lamictal	25	6
lorazepam	Ativan	12	3
mirtazapine	Remeron	20-40	8
olanzapine	Zyprexa	21-54	11
paroxetine	Paxil	21	5
phenelzine	Nardil	11.6	14
prazosin	Minipress	2-3	1
quetiapine	Seroquel	6	2
risperidone	Risperdal	3-20	4
sertraline	Zoloft	26	6
temazepam	Restoril	8-12	3
trazodone	Desyrel	9	2
venlafaxine	Effexor	12	3
ziprazidone	Geodon	7	2
zolpidem	Ambien	2.5	<1

The PI may prescribe a designated rescue medication in the event of symptoms that require it during or after the Experimental Session (e.g. insomnia or severe anxiety that does not respond to other non-pharmacologic management outlined in the treatment manual). Rescue medications may be a benzodiazepine, zolpidem, or other anxiolytic or sedative according to the physician's clinical judgment. SSRIs, SNRIs, and MAOIs should not be used as rescue medications.

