3.2 Exclusion Criteria

- 3.2.1 Current General Inpatient (GIP) hospice status
- 3.2.2 Patients currently receiving chemotherapy
- 3.2.3 Condition impairing oral intake or digestive absorption
- 3.2.4 Presence of a delirium diagnosed by the CAM (see Appendix A)
- 3.2.5 Significant suicide risk as defined by suicidal ideation with intend and a plan as endorsed on item 5 on the C-SSRS within the past month or at V0 (see Appendix A)
- 3.2.6 Current or past history of schizophrenia, psychotic disorder, bipolar disorder, delusional disorder, paranoid personality disorder, schizoaffective disorder, or borderline personality disorder, as assessed by medical history
- 3.2.7 History of allergic reactions attributed to compounds of similar chemical or biologic composition to psilocybin
- 3.2.8 Other personal circumstances and behavior that would limit compliance with study requirements, or judged by the study psychiatrist and/or principal investigator to be incompatible with establishment of rapport or safe exposure to psilocybin
- 3.2.9 Potential for adverse drug-drug interactions. Concomitant medications with significant potential to interact with study medications will be exclusionary if they cannot be tapered. These include the following:
 - Serotoninergic antidepressants
 - Centrally-acting serotonergic agents (e.g. MAO inhibitors)
 - Antipsychotics (e.g. first and second generation)
 - Mood stabilizers (e.g. lithium, valproic acid)
 - Aldehyde dehydrogenase inhibitors (e.g. disulfiram)
 - Significant inhibitors of UGT 1A0 or UGT 1A10

Any psychiatric medication will be tapered if possible in an appropriate fashion to avoid withdrawal effects. They will be discontinued long enough before the psilocybin Session to avoid the possibility of any drug-drug interaction (the interval will be at least five times the particular drug and active metabolites' half-life). See section 9 of the protocol for concomitant medications and tapering instructions.

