Participants will arrive at 8 am and complete the following assessments at V3, prior to receiving the medication: DS-II and HADS A and D. In addition, the lead therapist will complete the C-SSRS and the CAM.

The participant will take the study drug capsule (psilocybin 25 mg) under the therapy team supervision as soon as possible – typically between 9 and 9:30 am. No dose modifications will be necessary.

Blood pressure and heart rate will be measured at the following time-points after psilocybin administration: 30, 60, 120, 180, 240, 300, and 360 min.

During the psilocybin session, facilitators' role will be to monitor, assist and support patients while they are experiencing the effect of the medicine. The monitoring will focus on vital signs and distress level. The assistance and support, whether it's physical or emotional will follow patients' needs in a non-directive way. At the onset of the study agent effect, therapists will invite participants to lie down on the bed, put on eyeshades and put on headphones that will play a pre-selected play-list throughout the session. Therapists will encourage participants to focus inward and stay open to and present with whatever their inner experience is.

Psilocybin effect on perception and consciousness lasts 4 to 6 hours in most individuals. When the participant appears to have returned to his/her baseline psychological and physiological state, and he or she expresses a readiness to begin the discharge process, they will complete the Mystical Experience Questionnaire (MEQ-30) and the Challenging Experience Questionnaire (CEQ), and the Lead Therapist and co-investigator will determine if participant is safe and ready to be discharged home. Patients who are unable to be discharged home for medical or psychiatric

reasons will have the possibility to stay overnight at the hospice house for medical supervision. If for any reason the patient cannot stay at the hospice house and their situation requires medical supervision, arrangements would be made by the study team to admit them to a hospital.

Visit V4: Integration session #1 (patient's home or remote) – Day 1 (up to day 3)

The integration session 1 will occur the day after the psilocybin session (allowable window 3 days) and start with medical and psychological assessment as indicated on the schedule of assessments.

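### Four of the 26 entries in the Medication Tapering Table are rounded down and fall 4 to 8 hours short of the protocol's own five-half-life minimum

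*Combined protocol and SAP*

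**What the plan says.** Exclusion criterion 3.2.9 lists interacting drug classes, antipsychotics among them, that exclude a patient if they cannot be tapered. It then says of psychiatric medication: "They will be discontinued long enough before the psilocybin Session to avoid the possibility of any drug-drug interaction". Both 3.2.9 and section 9 give the minimum in the same words: "the interval will be at least five times the particular drug and active metabolites" half-life.

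The Medication Tapering Table in section 9 applies this to 26 drugs. It gives a half-life that includes active metabolites, either as one value or as a range, and a column headed "Days for Washout". The column does not say how a day is counted.

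An extra week for symptom stabilization is stated in two cases only: for MAO inhibitors, which also have a 14-day minimum, and for drugs outside the table ("The washout time for any drug not listed on the table will be at least 5 times the half-life", plus that week). Section 9 also provides a check by a clinician: "The study psychiatrist will be responsible for reviewing and confirming all medications collected during the study".

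**The concern.** The rule is a floor, so a conversion to whole days has to round up. Most of the table does. Four rows round down, so for those drugs the printed number of days and the rule it implements give different minimum intervals.

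The difference shows when rows are compared. Quetiapine works out at 1.25 days and is listed at 2; olanzapine works out at 11.25 and is listed at 11. Citalopram, with a half-life of 35 h, gets 8 days; clonazepam and mirtazapine, with half-lives of up to 40 h, also get 8.

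Two of the four drugs, olanzapine and risperidone, belong to a class named in 3.2.9. Section 5.2.1 makes absence of contraindicated medication a condition for dosing, so the washout figure has a practical use. The text does not say whether the rule or the table prevails when they differ, and staff may well work from the printed number.

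**Working it through.** **Inputs.** Half-lives and listed days come from the Medication Tapering Table in section 9. The multiplier of five comes from section 9 and criterion 3.2.9.

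**Formulas.** Required hours = 5 × upper half-life. Required days = required hours / 24. Shortfall = required hours − 24 × listed days.

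**Does the table use the upper limit?** Yes. Atomoxetine (5–24 h): 5 × 24 / 24 = 5.0, listed 5. Diazepam (20–70 h): 5 × 70 / 24 = 14.58, listed 15. Fluoxetine (7–9 days): 5 × 9 = 45, listed 45. Imipramine (6–18 h): 5 × 18 / 24 = 3.75, listed 4. Midpoints would give 3.02, 9.38, 40 and 2.5 days, which do not lead to the listed figures.

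**The four entries.**

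| Drug | Half-life (h) | Required h | Required days | Listed days (h) | Short by |
|---|---|---|---|---|---|
| Clonazepam | 30–40 | 5 × 40 = 200 | 8.33 | 8 (192) | 8 h |
| Mirtazapine | 20–40 | 5 × 40 = 200 | 8.33 | 8 (192) | 8 h |
| Olanzapine | 21–54 | 5 × 54 = 270 | 11.25 | 11 (264) | 6 h |
| Risperidone | 3–20 | 5 × 20 = 100 | 4.17 | 4 (96) | 4 h |

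**The other 22 entries.** None is short.
- Eighteen have a fractional result and are rounded up. In eight of these the fraction is below one half: alprazolam 2.29 to 3, bupropion 4.38 to 5, citalopram 7.29 to 8, lamotrigine 5.21 to 6, paroxetine 4.38 to 5, quetiapine 1.25 to 2, sertraline 5.42 to 6, ziprasidone 1.46 to 2.
- Two are exact: atomoxetine and fluoxetine.
- Phenelzine (5 × 11.6 / 24 = 2.42) is set at 14 days by the MAO-inhibitor rule.
- Zolpidem (5 × 2.5 = 12.5 h, or 0.52 day) is listed as less than one day, which is compatible with the rule but sets no definite number.

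**When the shortfall applies.** The half-life above which the listed days are too few is listed days × 24 / 5:
- clonazepam and mirtazapine: 192 / 5 = 38.4 h
- olanzapine: 264 / 5 = 52.8 h
- risperidone: 96 / 5 = 19.2 h

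At the midpoints of the ranges the requirement is 7.29, 6.25, 7.81 and 2.40 days (clonazepam, mirtazapine, olanzapine, risperidone), and none is short.

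**Drug remaining at the upper half-life.** Fraction = 2^−(listed hours / half-life):
- clonazepam and mirtazapine: 2^−(192/40) = 2^−4.8 = 3.6%
- olanzapine: 2^−(264/54) = 2^−4.89 = 3.4%
- risperidone: 2^−(96/20) = 2^−4.8 = 3.6%
- at exactly five half-lives: 2^−5 = 3.1%

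**Sensitivity to the meaning of a day.** Section 5.1.2 places dosing at V3 "typically between 9 and 9:30 am". If N listed days means N full drug-free calendar days before a 9 am dose, the shortest possible interval is 24N + 9 hours:
- clonazepam and mirtazapine: 192 + 9 = 201 h, against 200 h
- olanzapine: 264 + 9 = 273 h, against 270 h
- risperidone: 96 + 9 = 105 h, against 100 h

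On that reading all four comply.

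**The case against.** The strongest objection is that the table follows a pattern. Ten rows give a half-life range, and at the upper limit all ten agree with rounding to the nearest day (temazepam's 2.5 going up to 3). The rows rounded up despite a fraction below one half all give a single value. One could argue that a range taken at its upper limit already carries a margin, and that comparing olanzapine with quetiapine mixes two kinds of row. The pattern is real, but the document does not state it, and rounding to the nearest day cannot implement a minimum.

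Second, the shortfall needs a half-life in the top part of the range, roughly the top 16% of its width for clonazepam, 8% for mirtazapine, 4% for olanzapine and 5% for risperidone. It also needs a day to mean 24 elapsed hours. Both conditions stand. The second is itself unclear in the plan, so compliance depends on a convention that the plan does not give.

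Third, the rule in the text has no exception for listed drugs, and a psychiatrist reviews every medication. A reader who follows the text meets the floor. That limits the harm but leaves the printed figures in conflict with the rule.

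Fourth, the clinical weight is slight. Benzodiazepines are not on the 3.2.9 list, and section 9 allows them during or after the session: "Rescue medications may be a benzodiazepine, zolpidem, or other anxiolytic or sedative". Section 5.3 names risperidone or a similar antipsychotic among the supplies to be kept available after dosing. This stands in full and is why the point is minor.

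**Conclusion.** The concern holds as a minor correction. Four of 26 listed washouts are below the stated minimum by 4 to 8 hours, which is 4% of the required interval for clonazepam, mirtazapine and risperidone (8/200, 8/200, 4/100) and about 2% for olanzapine (6/270). The stabilization week does not cover them, since they are on the table and the plan does not treat them as MAO inhibitors.

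The conclusion assumes the upper end of each range, which is the basis the table itself uses, and 24-hour elapsed days. Without either assumption the shortfall goes. The arithmetic is certain; an actual under-washout in any patient is not shown. No endpoint, analysis or sample size is affected.

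**What to change.** Change four cells, subject to the study psychiatrist's confirmation: clonazepam 9, mirtazapine 9, olanzapine 12, risperidone 5. These give 216, 216, 288 and 120 hours against 200, 200, 270 and 100, so rule and table agree under either way of counting days.

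Add a line below the table that says how a washout day is counted (for example, 24 hours from the last dose to psilocybin administration) and that the five-half-life minimum governs if it and the table differ.

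The cost is four table cells, one sentence and at most one extra day of washout for a patient on one of these drugs.
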